- SIJ disruption was defined in the study as SIJ mediated pain in the context of asymmetric widening of SIJ on CT or Xrays or the presence of significant contrast leakage during diagnostic SIJ block
- Baseline Oswestry Disability Index (ODI) score of at least 30%
- Baseline Low back/buttock pain score of at least 50 on 0-100 mm visual analog scale
- Patient has signed study-specific informed consent form
- Patient has the necessary mental capacity to consent and participate and is physically able to comply with study protocol requirements
- Patient has medical insurance that covers this standard of care procedure and all other anticipated and unanticipated procedure related care.
- Patient's physician has decided that the best treatment for the patient's sacro-iliac disease is the LinQ system and the patient has agreed to the treatment.

Exclusion criteria:

- Inability to confirm that the pain is arising from the sacroiliac joint
- Current severe back pain due to other causes, such as lumbar disc degeneration, lumbar disc herniation, lumbar spondylolisthesis, lumbar spinal stenosis, lumbar facet degeneration, lumbar radicular pain, and lumbar vertebral body fracture
- SIJ pain secondary to inflammatory conditions, Other known sacroiliac pathology such as: Sacral dysplasia, Inflammatory sacroiliitis (e.g., ankylosing spondylitis or other HLA-associated spondylo-arthropathy), Tumor, Infection, Acute fracture, and Crystal arthropathy.
- Radicular pain extending beyond the buttock \geq 30mm on VAS
- Has complete resolution of pain from the diagnostic SIJ injection lasting 30 days or more
- Has had an injection with corticosteroid into the index SIJ within the last 30 days
- Has had any neuraxial injection with corticosteroid within the last 30 days

- Has greater than 50% pain relief from diagnostic medial branch blocks at the L4/5 and/or L5/S1 levels
- Has had a sacral radiofrequency ablation within the last 6 months
- History of any hardware placement within the sacrum or sacroiliac joint. Fusion at L5/S1 is allowed if screws/hardware are not within THE Sacroiliac joint. Any hardware or instrumentation that would obstruct the ability to access or place the Linq implant would be exclusionary.
- History of coccydynia or coccygectomy
- Clinical diagnosis of discogenic pain at L4/5 and/or L5/S1
- History of endometriosis or pudendal neuralgia
- History of recent (<1 year) major trauma to pelvis
- Chronic rheumatologic condition (e.g., rheumatoid arthritis)

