- Any condition or anatomy that makes treatment with the Linq Implant System infeasible
- Use of medications known to have detrimental effects on bone quality and soft-tissue healing (metabolic bone disease, induced or idiopathic)
- Prominent neurologic condition that would interfere with physical therapy
- Current local or systemic infection that raises the risk of surgery
- Patient currently receiving or seeking worker's compensation, disability remuneration, and/or involved in injury litigation.
- Patient is participating in an investigational study or has been involved in an investigational study within 3 months prior to evaluation for participation
- Patient with insurance coverage that does not cover the SI fusion*
- Implanted intrathecal pain pump

Withdrawal/Termination criteria:

- Patient's participation will only be withdrawn by their request. There are no criteria for termination of participation due to safety.

E. Specific methods and techniques used throughout the study

Study Design: The PainTEQ study is a prospective, multi-site, prospective, single arm study intended to collect clinical data outcomes data associated with the treatment of sacroiliac disease with the LinQ fusion procedure. Data will be collected using self-report measures including the visual analog scale (VAS) for pain assessment where the participant is asked to place a line perpendicular to the VAS line at the point that represents their pain intensity. Using a ruler, the score is determined by measuring the distance (mm) on the 10-cm line between the "no pain" anchor and the patient's mark, providing a range of scores from 0-100. Other self-report questionnaires will be administered including the Oswestry Disability Index (ODI) to measure low-back pain and disability, and the PROMIS 29 to measure physical, mental, and social health and well-being. The study team will also collect data including:

- Patient Satisfaction with Procedure
- Opioid consumption (Morphine Milligram Equivalents) at 1,3, 6, 12,18, 24 months.
- Serious adverse events and mortality as related to implantation of the device and events associated with recovery and rehabilitation
- Device related complications
- Satisfactory deployment (Defined as radiographic imaging of the implant within the SI joint. Procedure time
- Fluoroscopy time (in minutes)
- Blood loss
- Type of anesthesia (local; MAC; general)
- Patient demographics
 - Age
 - Gender
 - Race
 - BMI
 - Smoking (y/n)
 - Year of Pain

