 - Underlying diagnosis: degenerative sacroiliitis/sacroiliac joint disruption
 - Prior lumbar fusion (y/n)
 - Prior treatments (PT, FA, SIJ injection)

1. Timeline: Patients included in the study return for follow-up visits at 7-14 days, 1, 3 months, 6, 12, 18, and 24months post-treatment. Primary endpoint will be 6 month time point.
2. No randomization as treatment with the LinQ system will be performed regardless of whether the patient agrees to be in the research.

F. Risk/benefit assessment:

As appropriate, address the following parameters as each relates to the individual subject in the study.

1. Psychological risk: minimal, less than 1%
2. Social risk minimal, less than 1%
3. Potential benefit of participating in the study
 - a. To the individual subject and/or parent if any:

Improvement in the following domains:

 - a. Pain
 - b. Physical functioning
 - c. Emotional functioning
 - d. Patient global rating of improvement and satisfaction
 - e. Symptoms and adverse events
 - f. Patient disposition
 - b. To the population from which the subject is drawn: The study will provide

evidence to support a new treatment modality that is safe and effective. This

treatment modality also does not require repetition or multiple treatments unlike other treatments for sacroiliac joint dysfunction. It will also offer a salvage therapeutic option for patients who have failed other treatment modalities.

- c. To science, society, and humanity in general: Advancement of minimally invasive musculoskeletal techniques that may significantly reduce associated morbidity, mortality, and overall cost of treatment for chronic musculoskeletal related pain.

G. Location where study will be performed: Multisite

H. Collaboration: Multisite

I. Single IRB Review for a Multi-site study:

IRB local approval

J. Personnel who will conduct the study, including:

- 1. Indicate, by title, who will be present during study procedure(s): Study coordinator, attending physician, company representative, fellow physician (when available).
- 2. Primary responsibility for the following activities, for example:
 - a. Determining eligibility: PI, study attendings, senior trainees
 - b. Obtaining informed consent: Attendings at the study site including co-investigators, senior trainees at study site, and/or research coordinators
 - c. Providing on-going information to the study sponsor and the IRB: No Study Sponsors
 - d. Maintaining participant's research records: Research coordinator

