 - e. Completing physical examination: Attendings and trainees at study site
 - f. Taking vital signs, height, weight: Clinic staff
 - g. Drawing / collecting laboratory specimens: Not applicable
 - h. Performing / conducting tests, procedures, interventions, questionnaires: Attending physician and fellow physicians at study site
 - i. Completing study data forms: Research coordinator
 - j. Managing study database: Research coordinator

K. Adverse Event Monitoring

Adverse events and unanticipated problems will be ascertained and handled per standard of care as applies to any procedure. Problems that would be considered serious and reported to the IRB include infection, new skeletal fracture resulting from procedure, unanticipated post-operative admission, and neurologic injury and would be monitored for on an ongoing basis as per standard of care. The reporting timeframe would be within two weeks of incident to allow for appropriate additional diagnostic testing and treatment while maintaining study responsiveness to adverse events.

If patient experiences an adverse event or post-procedural problem, this will be treated per standard of care. This would include standard of care treatment of any related injury and potential device explanation. Patient may opt out of study at any time voluntarily. This would be monitored and discussed on an ongoing basis in the setting of an adverse event or post-procedural problem.

III. Subject Participation

A. Recruitment:

1. Potential study participants will come from the existing patient population of the investigators in each individual practice.

Recruitment can be performed by interventional pain providers and will be offered to anyone who is a candidate for the LinQ fusion procedure and meet the inclusion and exclusion criteria for the study. This research studies the LinQ system, a legally-marketed device, determined by that health care practitioner to be in the best interests of the patient. Patients will undergo treatment with the LinQ fusion procedure regardless of participation in the research. Therefore, the procedures being conducted because of the research are limited to data collection and the use of the LinQ system is not a research procedure.

B. Informed consent process and timing of obtaining of consent

The following study personnel may participate in the consent process: PI, co-Investigators, senior trainees, research assistants, and research coordinator.

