B. Procedures to protect subject confidentiality:

Patient identifiers may be included in master spreadsheet for reference to clinical chart if need arises for further review. Data will be de-identified with master spreadsheet containing patient identifiers linked to generated ID. A secondary spreadsheet will be generated containing pertinent study measures linked to the generated ID. The study coordinator will serve as the honest broker or buffer between master and secondary spreadsheets.

V. Data Analysis and Reporting

A. Statistical and Data Analysis:

Statistical analysis will include paired t-test of quantitative measures such as VAS pain score, Oswestry Disability Index, PROMIS 29, and quantitative secondary outcomes. ANOVA regression analysis will be performed to identify potential correlates of improved outcomes measures and adverse outcomes. IBM SPSS Statistics will be utilized to perform the analysis. Interim analysis will be performed on an anticipated monthly basis by a statistician. At no time will identifying information be transferred.

B. Outcome Measures:

i. Primary Outcome Measures

1. Binary success failure composite end point. A subject was considered a success if all of the following criteria were met
 - a. Reduction from baseline VAS SIJ pain by at least 20 mm
 - b. Absence of device related serious adverse events,
 - c. Absence of neurologic worsening related to the lumbosacral nerve roots,
 - d. Absence of surgical reintervention (removal, revision reoperation or supplemental fixation) for SIJ pain

ii. Secondary Outcome Measures

1. Improvement in baseline in VAS from baseline at 6 months
2. Oswestry Disability Index at 6 months follow up
3. PROMIS-29 at 6 months follow up
4. Patient Satisfaction with PGIC
5. Morphine milligram equivalent usage at all time points

C. Study results to participants:

Once final analysis completed, debriefing report will be given at follow up appointment or via telephone call. If no further contact maintained, copy of published manuscript will be sent to patients. Purpose of this will be to debrief patients as to study results.

D. Visit Schedule

	At least 7 days prior to Baseline	(within 4 weeks of surgery)									
Informed Consent	X										
Inclusion / Exclusion Review	X	X									
Urine Pregnancy test (if required)	X										
Surgery Information			X								
VAS	X	X		X	X	X	X	X	X	X	
PROMIS-29		X		X	X	X	X	X	X	X	
ODI	X	x		X	X	X	X	X	X	X	
Patient Satisfaction					X	X	X	X	X	X	

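### Among re-treatments, the month-6 primary composite counts only surgery as failure, and no follow-up item asks about SIJ injections or sacral ablations, so relief from these can be credited to the device

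*Protocol*

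**What the plan says.** **Endpoint.** Protocol II.E (Timeline) fixes the time: "Primary endpoint will be 6 month time point". Protocol V.B.i defines success by four conditions that must all hold: (a) VAS SIJ pain at least 20 mm below baseline; (b) no serious adverse event related to the device; (c) no worsening of lumbosacral nerve-root function; (d) "Absence of surgical reintervention (removal, revision reoperation or supplemental fixation) for SIJ pain".

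**Entry limits.** Protocol II.D excludes a patient who "Has had an injection with corticosteroid into the index SIJ within the last 30 days", and also one with a sacral radiofrequency ablation in the previous 6 months.

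**Data items.** The list in II.E opens with "The study team will also collect data including". After the procedure, the only pain treatment it names is "Opioid consumption (Morphine Milligram Equivalents) at 1,3, 6, 12,18, 24 months". SIJ injection appears as a data item only among the patient characteristics, under "Prior treatments (PT, FA, SIJ injection". The visit schedule (V.D) has follow-up rows for VAS, PROMIS-29, ODI, satisfaction, opioid medications and adverse events, and none for procedures on the joint.

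**Care after the procedure.** Protocol II.K says: "If patient experiences an adverse event or post-procedural problem, this will be treated per standard of care". No section bars injections or ablation during follow-up.

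**The concern.** Component (a) is a pain reading at one time point. Anything that lowers pain at that time can produce a success unless another component catches it. Component (d) catches re-treatment only when it is surgical.

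Take a patient with persistent pain who has a steroid injection into the index joint two weeks before the month-6 visit, or a sacral ablation at some time after the procedure, and then reads 20 mm below baseline. With no device-related serious event, no neurologic worsening and no reoperation, that patient is a primary success.

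The exposure is plausible. Recruitment can be done by interventional pain physicians from their own practices (III.A), and later problems are handled by usual care. With one arm, no comparison group receives the same treatments, so nothing offsets their contribution to the success rate. Opioid use is recorded at follow-up and can be examined. Injections and ablations can be examined only as far as they are found in charts.

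**Working it through.** **1. Sample size as planned.** Inputs from Protocol II.C: paired t-test, two-sided alpha 0.05, power 0.80, effect size 0.5, 20% loss, 50 enrolled. Exact noncentral-t power is 0.795 at n = 33 and 0.808 at n = 34, so the stated 34 reproduces. Allowing for loss, 34 / 0.8 = 42.5, rounded up to 43, so 50 is enough. Evaluable at the planned loss: 50 × 0.8 = 40. The point here does not alter the sample size.

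**2. How each treatment is handled.**

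| Treatment | Before entry (II.D) | After procedure: restricted? | After procedure: named in data list or schedule? | Counts as failure (V.B.i)? |
|---|---|---|---|---|
| Index-SIJ steroid injection | Excluded if within 30 days | No | No | No |
| Sacral radiofrequency ablation | Excluded if within 6 months | No | No | No |
| Opioids | No stated limit | No | Yes | No |
| Surgical reintervention for SIJ pain | Sacral or SIJ hardware excluded | No | Not as its own row | Yes, (d) |

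The baseline reading is protected from a recent injection or ablation and the month-6 reading is not. An ablation at any time between procedure and month 6, or an injection in the last 30 days before the month-6 VAS, lies inside the Protocol's own entry windows.

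**3. Effect of one affected patient.** Call a success affected if the patient would have missed 20 mm without the treatment. Each one adds 1/n to the success rate:

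- n = 40: 1/40 = 2.5 points
- n = 34: 1/34 = 2.9 points

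**4. Against sampling error.** The Protocol gives no success rate and no injection or ablation rate, so the rest is illustration. Assume 70% success and 5% of evaluable patients affected.

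- n = 40: bias 2/40 = 5 points. Exact (Clopper-Pearson) 95% CI for 28/40 is 53.5% to 83.4%; half-width (83.4 − 53.5)/2 = 15.0 points.
- n = 80 (assumed, if the registry enrolment mentioned in II.C continues): bias 4/80 = 5 points. The CI for 56/80 is 58.7% to 79.7%; half-width 10.5 points.

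A fixed affected share gives the same bias at either size while the interval narrows.

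**5. What a supportive rate would show.** If 2 of the 28 successes had been treated (assumed), the composite gives 28/40 = 70% and the supportive rate 26/40 = 65% (CI 48.3% to 79.4%). With success of 60% to 80% and 5% to 20% of successes treated (both assumed), the supportive rate at n = 40 is lower by 1/40 to 6/40, that is 2.5 to 15 points. This range counts every treated success, including patients already 20 mm better beforehand, so it measures the gap between two definitions and not the bias.

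**The case against.** The strongest case against has three parts.

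**Surgical-only is a deliberate and coherent choice.** A post-market study whose research procedures are limited to data collection may reasonably score pain as observed under usual care, and rules for intervening treatments are commonly left to the SAP. This stands as far as the primary definition goes, and is why the composite should stay as it is. It does not settle the data question: an SAP can add an analysis rule but cannot guarantee data that the Protocol never asks sites to collect.

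**Some of the data will exist.** The II.E list is open-ended, the electronic medical record is a named source (IV.A), a link to the clinical chart is kept (IV.B), and patients come from the investigators' own practices. Injections and ablations done there should be in the site record. This stands in part: it would be wrong to infer that the information is lost altogether. What is missing is a systematic, dated prompt and any route to treatment given elsewhere. An adverse-event entry might record the pain without its treatment.

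**No decision is shown to change.** The Protocol states no success threshold or performance goal, and every rate used above is assumed. This also stands and limits the weight of the point.

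Two stronger readings are tempting. One is that the composite fails patients for surgery alone. It does not: the VAS, device-event and neurologic components also fail patients, and the statement is true only among re-treatments. The other is that the gap contradicts the statement in II.F that the "treatment modality also does not require repetition or multiple treatments unlike other treatments for sacroiliac joint dysfunction". That sentence describes an expected benefit, not an objective or endpoint, and can be read as saying only that the implant procedure need not be repeated. It is no basis for this point.

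**Conclusion.** The point holds in a limited form. Under V.B.i, II.E and V.D as written, relief from an index-SIJ injection or sacral ablation can be credited to the device, and the study has neither a control group nor a systematic record with which to examine it.

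The size cannot be derived from the Protocol. Each affected patient is worth 2.5 points at 40 evaluable. At the planned size the total is probably below sampling error, but the confidence interval does not reflect it. The direction is upward on the assumption that these treatments do not raise pain.

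A reader might take the 2.5 to 15 point range as the overstatement. The document does not support that, because the range rests on assumed rates and includes patients who needed no help to reach 20 mm. Nor would a rate that counts only injections in the last 30 days form a bracket with the composite: an earlier injection that still gives relief would be a success in both, and the 30-day figure is an entry criterion that says nothing about when relief ends.

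This is worth correcting because it is cheap and cannot be reliably repaired later. It does not invalidate the study.

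**What to change.** 1. **Data.** At each existing follow-up visit, add a prompt for any index-SIJ injection or sacral ablation since the last visit, with dates and wherever it was given. The month-6 form should cover the interval since month 3. Add the matching row to the V.D schedule.
2. **Analysis.** Leave the composite unchanged. Prespecify, in the Protocol or SAP, a supportive month-6 success rate reported beside it, scoring as non-success any patient with an index-SIJ injection or sacral ablation between the procedure and the month-6 VAS.

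**Cost.** A few form lines at visits already planned and one sentence of analysis; no change in care or sample size. The supportive rate may be lower, partly because it reclassifies some patients who were already 20 mm better before a further treatment. It should be labelled a conservative sensitivity result and not an estimate of the bias.
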